2.3 STUDY TREATMENT

The study treatment will be delivery of nebulized sodium nitrite by nebulization at the dose of 45 or 90 mg.

Table 1 Dose Limiting Toxicity Criteria

Sign or Symptom	Moderate	Severe ¹
Bronchospasm/ wheezing	Symptomatic but not requiring therapy	Symptomatic and requiring therapy
Decrease in FEV_1	>15%	>25%
SBP ²	Systolic \geq 20 mm Hg drop from pre-dose baseline AND symptomatic, or SBP <80 mm Hg AND symptomatic	Systolic > 30 mm Hg drop from pre- dose baseline AND symptomatic or requiring fluid replacement or other therapy
Dyspnea	Causes more discomfort (than a mild, easily tolerated AE) and interrupts the subject's usual daily activities	Incapacitating and causes considerable interference with the subject's usual daily activities
Cough	Causes more discomfort (than a mild, easily tolerated AE) and interrupts the subject's usual daily activities	Incapacitating and causes considerable interference with the subject's usual daily activities
Hypoxia ³	$SaO_2 > 5\%$ drop from baseline AND symptomatic	$SaO_2 \geq 10\%$ drop from baseline or $SaO_2 < 88\%$ AND symptomatic

Percutaneous methemoglobin ^{4,5}	>5% and <7%	≥7%
Other drug-related signs or symptoms ⁶	Causes more discomfort (than a mild, easily tolerated AE) and interrupts the subject's usual daily activities OR CTCAE v.4 ⁶ Grade 2 toxicity	Incapacitating and causes considerable interference with the subject's usual daily activities OR CTCAE v.4 ⁶ Grade 3 or 4 toxicity

AE = adverse event; CTCAE = Common Toxicity Criteria for Adverse Events; DLT = dose limiting toxicity; SBP = systolic blood pressure; SaO₂ = oxygen saturation (hemoglobin)

1. Severe DLT seen in any subject which is deemed to be study drug-related will preclude further dosing with nebulized sodium nitrite for that subject.
2. Moderate or Severe SBP without symptoms will be continuously monitored with BP measurements every 5 minutes. Symptomatic refers to dizziness or fainting. Discontinuation of further dosing or dose escalation will be based upon follow up blood pressure measurements, subject symptoms and physician-investigator discretion (see Stopping Rules).
3. Moderate or Severe SaO₂ without symptoms will be continuously monitored and recorded every 5 minutes until return of saturation > 92%.
4. Elevated percutaneous methemoglobin levels measured by pulse co-oximeter will be continuously monitored and confirmed by venous methemoglobin level. Follow up will be based upon the clinical decision of the operating physician and will be documented as such.
5. A single occurrence of venous methemoglobin levels >5% in an individual subject will result in no further dosing for that individual subject for the remainder of the study period.
6. Common Terminology Criteria for Adverse Events v. 4.0 ([CTCAE](#)). CTCAE criteria will be applied if considered related to study drug and confirmed on repeat testing.

2.4 DURATION OF FOLLOW-UP: All subjects will be followed for 14 days +/- a 5 day window after completion of the study treatment. Subjects removed from study for unacceptable adverse events will be followed until resolution or stabilization of the adverse event.

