2.5 SAFETY MONITORING

Prior studies suggested that hypotension and methemoglobinemia may occur with the use of sodium nitrite. The study treatment of inhaled nitrite will be used safely with careful monitoring and prompt discontinuation of the study treatment in response to systemic hypotension with definitions of dose limiting toxicity. The presence of severe DLT deemed to be study-drug related will lead to a discontinuation of the study treatment.

Following study drug treatment, subjects will be evaluated as an outpatient at the clinic on Day 42 (+/- 5 day window). Interval study visits (days 7, 14 and 28) have been included in the study design to ensure subject safety. Subjects will be followed for evidence of acute or delayed adverse effects from the study treatment and to assess their clinical status. All adverse events experienced by subjects will be collected from beginning of visit 1 through final study visit. Study subjects will be routinely questioned about adverse events at study visits. The study investigators will evaluate all subject reported and observed AEs. All untoward medical occurrences observed in subjects receiving the study drug will be recorded on the participants' adverse event worksheets by the study coordinator under the supervision of the principal investigator. AEs occurring pre-treatment, during active treatment and post-treatment will be summarized separately. Subjects continuing to experience toxicity at the off study visit may be

contacted for additional assessments until the toxicity has resolved or is deemed irreversible. If possible, symptoms should be managed symptomatically. In the case of toxicity, appropriate medical treatment should be used.

In addition to these formal evaluations, subjects will be encouraged to immediately contact the study investigator and/or the study coordinator with questions, concerns, or to report new symptoms that occur during their study participation. If appropriate, based upon the evaluation, medical treatments will be provided to subjects, including appropriate referral to physicians or other services at the UPMC.

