2.6 STOPPING RULES

Two distinct scenarios in which subjects must be removed from the study are anticipated.

First, the subject experiences a CF respiratory exacerbation marked by a persistent drop in FEV1 >15% that is not temporally associated with nebulized sodium nitrite administration. The drop in FEV1 would be seen on the first set of spirometry at a visit, prior to dosing of nebulized sodium nitrite for that day. In this case, subjects will be removed from the study and referred to their pulmonologist for treatment of the CF respiratory exacerbation.

Drop in FEV1 >15% on the first set of spirometry, prior to drug administration, on any study visit when compared with baseline spirometry collected at screening.

In the second scenario, nebulized sodium nitrite is associated with a dose-dependent intolerance that will be seen at the dose escalation visit 2, or after receiving the first dose of drug on visit 1. Specific intolerances of concern are acute bronchospasm, hypotension or methemoglobinemia. In this case, if any one of the below occurs at the 45 mg dose, subject will be removed from the study; if any occur at the 90 mg dose, the subject will return to the previously tolerated dose of 45 mg.

Specific criteria for dose-dependent intolerance are:

Decrease in FEV1 by >15% between measurements on an individual study visit.

A decrease in systolic BP > 40 mmHg drop from pre-dose baseline or to <80mmHg and symptomatic.

SaO₂ drop below 88% and symptomatic or SaO₂ desaturation > 5% from baseline and symptomatic

A single occurrence of venous methemoglobin level >5%

Any serious adverse event thought to be possibly related to the study treatment

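### At 90 mg, some toxicities are ordered both to end dosing and to step down to 45 mg, and no passage says which order governs

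*Combined protocol and SAP*

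**What the plan says.** **Rules that end dosing**

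- Section 2.3, Table 1, footnote 1: "Severe DLT seen in any subject which is deemed to be study drug-related will preclude further dosing with nebulized sodium nitrite for that subject".
- Section 2.5: "The presence of severe DLT deemed to be study-drug related will lead to a discontinuation of the study treatment".
- Section 2.3, Table 1, footnote 5: one venous methemoglobin above 5% "will result in no further dosing for that individual subject for the remainder of the study period".

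None of these is restricted to one dose level. Table 1 classes as severe an FEV1 decrease above 25%, symptomatic SaO2 below 88%, and a symptomatic systolic drop above 30 mm Hg.

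**Rules that step the subject down**

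Section 2.6, repeated in 5.5.2, lists intolerance criteria. At 45 mg, any of them removes the subject. Otherwise, "if any occur at the 90 mg dose, the subject will return to the previously tolerated dose of 45 mg". The list includes:

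- "A single occurrence of venous methemoglobin level >5" (percent);
- "Decrease in FEV1 by >15% between measurements on an individual study visit", with no upper limit;
- SaO2 "drop below 88% and symptomatic";
- "A decrease in systolic BP > 40 mmHg drop from pre-dose baseline or to <80mmHg and symptomatic".

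For a sustained FEV1 fall after the first 90 mg dose, 2.13.1 also keeps the subject on 45 mg. Section 2.14.2 does so if recovery conditions are met after 4 hours and a 45 mg re-challenge is tolerated. Visit 2 in 2.2.1 sets similar re-challenge conditions. Neither re-challenge passage excludes a severe DLT or a raised methemoglobin.

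**The concern.** Safety is the trial's objective, and 2.5 names hypotension and methemoglobinemia as the anticipated hazards. The rule for what happens after a serious reaction should therefore have only one reading. At 45 mg it does, because every route leads to stopping. At 90 mg, for some events, staff who follow one mandatory sentence breach another.

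Following the step-down rule re-exposes a subject whom another rule bars from the drug. After the observed re-challenge, the remaining doses are taken at home (2.10). Two subjects with the same event could also be handled differently, with either choice defensible from the text.

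**Working it through.** This is a comparison of text; one small calculation sizes the exposure.

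**Step 1. Apply both sets of rules to the same event at 90 mg** (drug-related where footnote 1 requires it).

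| Event at 90 mg | Footnotes and 2.5 | 2.6 and 5.5.2 | Result |
|---|---|---|---|
| Venous methemoglobin >5% | Stop (footnote 5) | 45 mg | Conflict |
| FEV1 fall of 26% | Stop (severe) | 45 mg | Conflict |
| FEV1 fall of 20% | Moderate, no stop order | 45 mg | No conflict |
| SaO2 of 87%, symptomatic | Stop (severe) | 45 mg | Conflict |
| SBP drop of 45 mm Hg, symptomatic | Stop (severe), but see footnote 2 | 45 mg | Ambiguous |
| SBP drop of 35 mm Hg to 85, symptomatic | Stop (severe), but see footnote 2 | Not listed | No step-down order |

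For methemoglobin, the event, sample type and threshold are identical in both places. For FEV1, the conflict arises because the step-down criterion starts above 15% and has no ceiling, so it takes in the severe range above 25%.

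**Step 2. Look for a tie-breaker.**

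- *Footnote 2* is attached to the SBP row. It bases discontinuation on follow-up pressures, symptoms and investigator judgement, and refers to the Stopping Rules. It says nothing about FEV1, SaO2 or methemoglobin.
- *Footnote 4* leaves follow-up of raised percutaneous readings to the physician. It does not qualify footnote 5, which concerns venous values.
- *Sections 2.14 and 2.14.2* let the investigator withdraw a subject, but do not rank the rules.
- *Section 2.14.2* leaves methemoglobin out of its day 7 re-challenge triggers. That fits footnote 5, but 2.6 and 5.5.2 still order a return to 45 mg for any listed event.

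None of these settles methemoglobin, FEV1 or SaO2.

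**Step 3. Size the exposure.** Inputs are Visit 2 on day 7 and Visit 4 on day 28, each ±1 day (2.11), two doses a day (2.10), and 45 mg per dose.

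- Under footnotes 1 and 5: 0 further doses.
- Under 2.6, nominal: (28 − 7) × 2 = 42 doses; 42 × 45 = 1,890 mg.
- Shortest window: (27 − 8) × 2 = 38 doses; 38 × 45 = 1,710 mg.
- Longest window: (29 − 6) × 2 = 46 doses; 46 × 45 = 2,070 mg.

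These are ceilings, assuming the re-challenge is tolerated and nothing later stops treatment.

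**Step 4. Check the plan's power figure.** Section 2.15.1 gives 82% power at n = 33 for a one-sided binomial test of 0.06 against 0.20 (0.06 + 0.14). The exact calculation rejects at 5 or more events, with P(X ≥ 5 | 0.06) = 0.0454 and P(X ≥ 5 | 0.20) = 0.818. The figure reproduces and does not depend on this point.

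**The case against.** **Moderate reactions step down and severe ones stop.** This is a sensible reading and may be what was intended. No passage says it, however, and it cannot resolve methemoglobin, where both rules use the same threshold.

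**Blood pressure is not a plain contradiction.** This stands. Only the first sentence of footnote 2 is confined to changes without symptoms. Its last sentence weighs symptoms and points to the Stopping Rules, so it can be read as governing the SBP row. Footnote 1 and 2.5 still point to stopping. The text is therefore ambiguous, which is less than an unaddressed pair of opposite orders.

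**The practical risk is limited.** Much of this stands. The lower dose has already been taken for a week, re-challenge follows observation and recovery conditions, monitoring is repeated, and the investigator may withdraw anyone. Methemoglobin did not exceed 3% in the studies cited for dose selection (1.3.3) and stayed below 3.5% in CS01 at doses up to 176 mg (5.1.1). These safeguards make the 42 doses an extreme, but they do not decide which rule applies.

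**Stronger readings that the documents do not support:**

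- *That one reclassified subject could change the binomial result.* Section 2.15.1 does not define discontinuation, and the cut-off depends on the number analysed. Five events reject at n = 33 (p = 0.0454) but not at n = 34 (0.0506) or at the planned enrolment of 35 (0.0563), where six are needed (0.0168 at n = 35). With no event rate for these toxicities at 90 mg, no such consequence can be claimed.
- *That the 40 mm Hg re-challenge limit is an error and should be 30.* An asymptomatic, untreated drop of 31 to 40 mm Hg is neither a Table 1 DLT nor on the 2.6 list. A tighter limit would be a preference.
- *That every severe DLT is ordered back to 45 mg.* Treated bronchospasm and incapacitating cough or dyspnea are not named on the 2.6 list.

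**Conclusion.** The contradiction is real and should be fixed. It holds firmly for venous methemoglobin above 5%, and for a drug-related FEV1 fall above 25% or symptomatic SaO2 below 88%, all at 90 mg. For a symptomatic systolic drop above 40 mm Hg the protocol is ambiguous, not plainly contradictory.

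For an affected subject the difference is no further drug against a ceiling of about 42 doses of 45 mg (38 to 46 with visit windows). How many subjects would be affected cannot be estimated: no rate at 90 mg is given, and the methemoglobin event is likely uncommon. The consequence is for subject safety and consistent conduct. No power or sample-size figure changes.

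**What to change.** State in 2.3, and repeat in 2.6 and 5.5.2: *A drug-related severe DLT under Table 1, or a venous methemoglobin >5%, ends dosing at either dose and overrides step-down and re-challenge.*

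Then bring the other text into line:

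- Remove methemoglobin above 5% from the events that return a subject to 45 mg.
- In 2.2.1 (Visit 2), 2.6, 2.13.1, 2.14.2 and 5.5.2, limit step-down and re-challenge to intolerance that is not a drug-related severe DLT, for example an FEV1 fall above 15% and up to 25%.
- State whether the precedence also applies to SBP despite footnote 2.
- Leave the 40 mm Hg re-challenge limit as it is.

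The cost is a wording amendment with IRB approval. Because it bears on subject safety, 6.3.1 calls for a Protocol Amendment to the IND before implementation. No new visits or measurements are needed. A few subjects may stop instead of continuing at 45 mg, which would leave slightly less on-drug data between day 7 and day 28.

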was seen at 90 mg. This study included dosing subjects with mild hypoxia (such as might be seen in patients with end stage lung disease) and no interaction was seen between hypoxia and nebulized nitrite. Methemoglobin did not exceed 3% in these studies. Subsequently, in a study of 36 participants with pulmonary hypertension, no increase in methemoglobin was seen with 90 mg doses (17). Another study on heart failure with preserved ejection fraction found no increase in methemoglobin as compared to control (18). Methemoglobin levels above 30% of total hemoglobin can cause shortness of breath due to the reduced oxygen carrying capacity, and levels above 50% can lead to seizures and death(19). In these studies, nebulized sodium nitrite was dosed up to every 8 hours for 6 days. Thus at doses up to 90mg, nebulized sodium nitrite appears safe in healthy subjects for dosing. Additional, unpublished safety data is available from Phase 2b clinical trials that were terminated with the sale of the sponsor company. More than 30 subjects with pulmonary arterial hypertension have been treated for as long as 12 months with no treatment related serious adverse events. In the recently completed studies of inhaled nitrite for pulmonary hypertension, doses of 46 or 80 mg four times daily were reportedly well tolerated for up to 16 weeks. Since initial submission of this protocol, additional safety data in 36 patients with pulmonary hypertension and heart failure with preserved ejection fraction have been published. In these studies, one subject was withdrawn due to asymptomatic hypotension, and the only side effect reported was occasional self-limited cough (17, 18). Regarding the doses where nitrite may have antimicrobial activity, we estimate that with a dose of 46 mg in a high efficiency nebulizer no less than 50% of the dose will reach the lower airways. Assuming a volume of distribution in the airway surface liquid of at most 7 mL, we estimated that the initial sodium nitrite concentration in the airway after nebulization of a 46 mg dose will be 47 mM, and with 80 mg, 82 mM. In the CF airway, assuming surface liquid depletion, these are likely conservative estimates and the immediate post-deposition concentration may be higher. Importantly, these estimated concentrations are above the concentrations that we found reduce biofilm growth of *P. aeruginosa* (1 log reduction at 15 mM)(7). Based on these considerations, in this safety and proof of concept study, we will target dosing above the concentrations necessary for an anti-microbial effect and two fold below the maximal tolerated dose in normal volunteers. Dosing will be 45 mg (controlled by the nebulizer) for the first week to provide multiple day safety data prior to observed escalation to the target 90 mg dose for the remaining three weeks of the study

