Experimental Procedure (visit 2/day 7 (+/- 1day)): This visit will take approximately 5-7 hours. Subjects will arrive and complete the CFQ-R CF Questionnaire. FENO will be measured as above. If the subject had no serious adverse events for the first seven days of the 45 mg dose of nebulized sodium nitrite, and has stable systemic blood pressure and FEV₁ on presentation to the Day 7 visit, an electronic nebulizer will be used to deliver 90 mg of nebulized sodium nitrite. Subjects will be monitored closely for the next two hours, including percutaneous measurements of oxygen saturation and methemoglobin levels, recorded at minutes 15, 30, 60 and 120, and noninvasive systemic blood pressure measurements every 15 minutes. If percutaneous methemoglobin measurements exceed 5%, they will be confirmed by venous blood measurement. Spirometry will be repeated at 30 and 120 minutes following nebulized sodium nitrite administration. If nebulized sodium nitrite is tolerated, then the subject will be dispensed an 8 day supply of 90 mg nebulized sodium nitrite dosed two times daily and discharged from the CTRC, CHP or the Emphysema Research Center in Montefiore. If the 90 mg dose of nebulized sodium nitrite was not tolerated, the subject will be observed. If FEV₁ returns to baseline in 4 hours and subject's SaO₂ is not greater than 5% drop from baseline and systolic BP is not greater than 40 mm Hg drop from pre-dose baseline, the subject will be re-challenged at this visit with a 45 mg dose of nebulized sodium nitrite and the observation protocol of blood pressure measurements, spirometry and percutaneous oxygen saturation measurement will be repeated.

Experimental Procedures (visit 3/day 14(+/- 1day)): This is a safety and tolerability visit and will take approximately 1 hour. Subjects will complete the CFQ-R and spirometry. An oral wash will be collected, and then a sputum sample will be collected. If the subject cannot spontaneously expectorate, then sputum induction will be done. The subject will then be discharged with a 15 day supply of nebulized sodium nitrite.

Experimental Procedures (visit 4/day 28(+/- 1day)): This visit will take approximately 1.5 hours. Subjects will complete the CFQ-R and spirometry. Expectorated or induced sputum will be collected, an oral wash will be collected, and FE_{NO} measured as above. Sputum will be used to measure nitrite concentration and quantitative bacterial load.

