If subjects spontaneously expectorate, then sputum induction will not be done. After sputum induction, subjects will wait a minimum of 30 minutes prior to nebulization of nebulized sodium nitrite because sputum induction can cause temporary bronchoconstriction and this might confound the safety assessment of nebulized sodium nitrite. The amount of wait time will be determined by the physician investigator at the time of visit. Sputum induction will be done on Study days 0, 14, 28, and 42. If no further administration of nebulized sodium nitrite is planned during the visit (Days 14, 28, and 42), subjects may leave after sputum induction if they are not symptomatic.

Nebulization of Drug: nebulized sodium nitrite will be nebulized via electronic nebulizer with direct observation by a study physician or nurse coordinator on day 0, and at dose escalation by a study physician or nurse coordinator on day 7 in the CTRC, CHP or an Emphysema Research Center room in Montefiore. Subsequent doses will be self-administered by the subjects two times daily at home.

CFQ-R Questionnaire: Subjects will complete this standard and validated questionnaire on paper. Results of the CFQ-R will be confidentially stored electronically. Original paper will be maintained and stored in the locked Pulmonary Medicine Allergy and Immunology office.

NIOX device: Subjects exhale slowly through the device as guided by a small video screen with a smiling cloud icon. Disposable filters are used for each subject to minimize infection control concerns with the device. NIOX data will be recorded on days 0, 7 and 28.

Phlebotomy: Blood will be drawn by trained personnel at the screening visit (and day 0 if labs require repeating). Peripheral blood for confirmatory methemoglobin level will be obtained if percutaneous methemoglobin levels exceed 5%.

Vital sign measurements: Pulse, systemic blood pressure, temperature, respiratory rate and pulse oximetry will be measured noninvasively by trained study personnel using standard clinical equipment. All these values will be measured on screening visit and days 0, 7 and 42 (exit exam). On days 0 and 7 when nebulized sodium nitrite is being administered with observation, percutaneous measurements of oxygen saturation and methemoglobin levels will be measured for two hours after delivery. Noninvasive systemic blood pressure measurements will be taken every 15 minutes for the first two hours.

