2.11 SCHEDULE OF ACTIVITIES

Study Phase	Screening	Treatment				Follow-Up Monitoring
Visit Type	Outpatient	Outpatient				
Study Day	day -28 to -2	(visit 1) day 0 - +/- 1 day	(visit 2) day 7 - +/- 1 day	(visit 3) day 14 - +/- 1 day	(visit 4) day 28 - +/- 1 day	(visit 5) day 42 - +/- 5 day
Informed Consent	X					
Medical History and Demographics	X					
I/E Criteria	X					
Tolerability Determination for Dose Escalation			X			
Physical Exam	X	X				X
Vital Signs (Pulse, systemic blood pressure, temperature, respiratory rate and pulse oximetry)	X	X	X			X
Non-invasive blood pressure measurement		X	X			
Oxygen Saturation		X	X			
Laboratory Tests***	X					
Urine Pregnancy Test Δ	X					
Spirometry	X	X	X	X	X	X
Sputum Collection		X		X	X	X
FeNO		X	X		X	
oral wash		X		X	X	X
Percutaneous metHgb Level§		X	X		X	
CFQ-R symptom assessment		X	X	X	X	X
AE Assessment		X	X	X	X	X
Interval History Assessment						X

Δ Urine pregnancy test will be performed only on female of childbearing potential. *** Clinical laboratory tests may be repeated on study visit 1 if screen lab results deemed clinically significant and warrant repeat testing or inadvertently not collected at screen visit § Methemoglobin

(metHgb) levels: will be measured and recorded at the following time points: pre-dose, approx. 5, 15, 30, 60, and 120 minutes post each dose of nebulized sodium nitrite. If percutaneous measurements exceed 5%, then a venous blood sample will be drawn for confirmation. Peripheral blood for confirmatory methemoglobin level will be obtained 60 minutes after nebulization on study days 0 and 7 and for a final methemoglobin level on day 28.

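### After one venous methemoglobin above 5% at 90 mg, Table 1 footnote 5 ends dosing while 2.6 and 5.5.2 return the subject to 45 mg, and nothing says which rule prevails.

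*Combined protocol and SAP*

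**What the plan says.** Three places in the combined protocol and SAP give the action for a single confirmed methemoglobin above 5%.

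- **Section 2.3, Table 1, footnote 5:** "A single occurrence of venous methemoglobin levels >5% in an individual subject will result in no further dosing for that individual subject". The sentence goes on to cover the rest of the study. It carries no dose condition.
- **Section 2.6:** the intolerance criteria include "A single occurrence of venous methemoglobin level >5" (percent). If a criterion is met at 45 mg, the subject leaves the study. For the higher dose, "if any occur at the 90 mg dose, the subject will return to the previously tolerated dose of 45 mg".
- **Section 5.5.2, Stopping Rule:** repeats the rule and the criteria of 2.6.

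Two further places deal with intolerance of 90 mg on day 7.

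- **Section 2.2.1, visit 2:** "If the 90 mg dose of nebulized sodium nitrite was not tolerated, the subject will be observed". A 45 mg re-challenge the same day then depends on FEV1, oxygen saturation and systolic pressure.
- **Section 2.14.2:** opens the re-challenge to hypotension, a sustained FEV1 fall or desaturation. Methemoglobin is not named there, although it stands in the day 0 list just above.

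**The concern.** The analyte, the sample, the threshold and the number of occurrences are the same, but the prescribed actions are opposite. Staff who follow 2.6 give more drug to a subject whom footnote 5 bars from it. Staff who follow footnote 5 withhold a step-down that 2.6 prescribes. Either choice departs from the written protocol.

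Safety is the objective of the trial, and 2.6 names methemoglobinemia among its three intolerances of concern, so its place in that list does not look like a slip. After a step-down, "Subsequent doses will be self-administered by the subjects two times daily at home".

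The choice of rule can also reach the safety tables. Section 2.15.2 calls for a separate summary of adverse events leading to withdrawal, and the same laboratory result could fall inside or outside it.

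**Working it through.** **Step 1. Compare the rules by dose.**

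| Source | Venous level above 5% at 45 mg | Venous level above 5% at 90 mg |
|---|---|---|
| Table 1 footnote 5 | No further dosing | No further dosing |
| 2.6 and 5.5.2 | Removed from study | Return to 45 mg |
| 2.14.2, day 0 list | Treatment discontinued | Not applicable |
| 2.14.2, day 7 paragraph | Not applicable | Methemoglobin not named |
| 2.2.1, visit 2 | Not applicable | Re-challenge for 90 mg not tolerated; type of intolerance not specified |

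The conflict is confined to 90 mg.

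**Step 2. Look for a text that sets precedence.**
- Footnote 4 leaves follow-up of a raised percutaneous level to the physician. It does not rank footnote 5 against 2.6.
- Footnote 2 refers to the stopping rules, but for blood pressure only.
- A tiered reading (step down if moderate, stop if severe) does not help. Footnote 5 acts above 5%, the same threshold as 2.6, so the rules disagree over the whole range above it.
- The day 7 paragraph of 2.14.2 fits footnote 5 by omission, but states no rule for methemoglobin.

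**Step 3. Check that the event can be observed.** Day 7 is the first 90 mg dose. The footnote to the schedule in 2.11 calls for venous blood "60 minutes after nebulization on study days 0 and 7 and for a final methemoglobin level on day 28". Sections 2.2.1 and 2.10 call for it when the percutaneous level exceeds 5%. Either way, a level above 5% can be confirmed on day 7 with three weeks of dosing still planned. A level above 5% that first appears on day 28 has no consequence for dosing, because treatment ends then.

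**Step 4. Size of the difference after a day 7 event.** Inputs are twice-daily dosing (2.2.1, 2.10), visits on days 7 and 28 with windows of 1 day each (2.11), and a 45 mg step-down dose (2.6).
- Footnote 5: 0 doses, 0 mg.
- 2.6, nominal: 28 − 7 = 21 days; 21 × 2 = 42 doses; 42 × 45 = 1,890 mg.
- 2.6, shortest: 27 − 8 = 19 days; 38 doses; 1,710 mg.
- 2.6, longest: 29 − 6 = 23 days; 46 doses; 2,070 mg.

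These figures use the four-week regimen of 2.2.1. The synopsis gives 56 days as the duration of treatment, which does not match the visit plan.

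**Step 5. How likely and how grave.** The documents give no rate in cystic fibrosis. Section 1.3.3 reports levels not above 3% in the healthy-volunteer studies and says that "in a study of 36 participants with pulmonary hypertension, no increase in methemoglobin was seen with 90 mg doses". Section 5.1.1 reports levels below 3.5% in all subjects of the first-in-man study, which went up to 176 mg. Section 1.3.3 places shortness of breath above 30% and seizures or death above 50%. The trigger is 5/30, one sixth of the lower figure.

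**Step 6. Effect on the primary inference.** Section 2.15.1 rests on discontinuation for an FEV1 fall above 15%. Its figure reproduces: with 33 subjects, null rate 0.06, alternative 0.06 + 0.14 = 0.20 and rejection at 5 or more events, exact power is 0.818 (stated 82%) and the attained one-sided level is 0.0454. Methemoglobin does not enter it.

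**The case against.** The strongest reply is that the protocol already leans toward stopping. Footnote 5 is specific to this event, whereas 2.6 uses a general clause for any listed criterion. Section 2.14.2 leaves methemoglobin out of the day 7 re-challenge, and the visit 2 recovery conditions match its three triggers. The investigator may discontinue anyone at any time (2.14) and must withdraw a subject when continuing is not in that subject's interest (2.14.2). The step-down dose is half of 90 mg, and the subject has already taken it for about a week. All of this stands, and it makes harm unlikely. It does not remove the conflict: 2.6 and 5.5.2 expressly include the trigger and expressly prescribe 45 mg.

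Four stronger readings are tempting, but the documents do not support them.

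- *That a re-challenge would go without methemoglobin monitoring.* Section 2.2.1 says that "the observation protocol of blood pressure measurements, spirometry and percutaneous oxygen saturation measurement will be repeated", which omits it. But the schedule footnote in 2.11 and Section 2.12.4 require methemoglobin before and up to 120 minutes after each dose.
- *That the conflict creates the gap in testing between days 7 and 28.* Every subject follows that schedule, including those who stay on 90 mg.
- *That the study of 36 participants caps the number of events in this trial.* It reports no increase, not a count above 5%, and not in cystic fibrosis. An upper confidence limit multiplied by 35 is an expected count at that limit, not a maximum.
- *That every step-down after a severe toxicity is equally contradictory.* Footnote 1 and 2.5 do stop dosing for severe drug-related toxicity, and some such events also meet 2.6. There a tiered reading is possible though unstated, and footnote 2 leaves discretion for blood pressure. At most, that overlap needs clarifying.

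**Conclusion.** The plan is wrong as written on one trigger at one dose. For a venous methemoglobin above 5% at 90 mg, the written rules cannot both be followed. For a day 7 event the difference is 0 against about 42 further doses of 45 mg (range 38 to 46), assuming that the four-week regimen of 2.2.1 applies and that the subject takes every dose.

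The practical risk is probably small. It rests on earlier levels below the trigger in people not described as having cystic fibrosis, on a trigger far below the symptomatic range, and on the investigator's power to withdraw a subject. The point concerns conduct and safety reporting. It does not touch the FEV1 endpoint or the sample size.

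**What to change.** In 2.6 and 5.5.2, take a venous methemoglobin above 5% out of the 90 mg step-down and state that it ends dosing at either dose, as in footnote 5. In 2.2.1, visit 2, add that such a subject is not re-challenged on day 7. Section 2.14.2 already fits and needs no change on this point.

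The cost is an amendment of wording, with no added procedures or subjects. It needs IRB approval and, if judged to affect subject safety significantly, an IND amendment submitted before it takes effect (6.3.1). The clinical downside is that a rare subject who might have continued safely at 45 mg stops.

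The change should not be widened to bar step-down for all Table 1 severe events. That would remove the 45 mg option in 2.6 for symptomatic saturation below 88%, symptomatic systolic falls above 40 mm Hg and drug-related FEV1 falls above 25%. The last of these could also change the discontinuations on which 2.15.1 relies.
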